3.3.2.2 Secondary Outcomes

1) Severity of AKI

Within 7 days postoperatively, the postoperative AKI classification was assessed according to KDIGO criteria based on AKI severity (KDIGO staging: Stage 1/2/3):

Stage 1: Serum creatinine elevation ≥ 0.3 mg/dl or 1.5 – 1.9 times the baseline value, or urine output < 0.5 mL/(kg · h) for 6 – 12 hours;

Stage 2: Serum creatinine levels increased 2.0 – 2.9-fold, or urine output < 0.5 mL/(kg · h) for ≥ 12 hours;

Stage 3: Serum creatinine elevation ≥ 3.0 mg/dl, or ≥ 3 times the baseline value, or urine output < 0.3 mL/(kg · h) for ≥ 24 hours, or requiring RRT.

The AKI severity grading was determined by the highest KDIGO stage achieved within 7 days postoperatively.

2) Renal replacement therapy

The proportion and duration of acute RRT required during hospitalization.

3) Renal function recovery

In patients with AKI, those who still meet AKI criteria on postoperative day 7 were defined as having persistent AKI. The time from diagnosis to the first recovery of serum creatinine to within 1.5 times the baseline level without the need for RRT was calculated as the creatinine recovery time.

4) Long-term renal function

Serum creatinine and eGFR at 30 days postoperatively.

5) Autonomic nervous function

5-minute electrocardiogram (ECG) signals were collected preoperatively and at 24 hours, 48 hours, and 72 hours postoperatively, with heart rate variability (HRV) analyzed using Kubios HRV software.

6) Early recovery quality

Postoperative early recovery quality was systematically evaluated from multiple dimensions. Mechanical ventilation duration was defined as the time from the first successful extubation after surgery. The vasoactive drug index was calculated daily within 7 days postoperatively, with peak values and mean values recorded separately. Delirium incidence was assessed daily using either

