3.3.2.3 Basic Clinical Indicators

Prior to randomization of patients, trained investigators collected the following baseline data. All measurements were based on the most recent test conducted after hospital admission and prior to surgery, and must be completed before randomization.

Demography and anthropometry: age, gender, height, weight, body mass index (BMI), ASA classification.

Cardiac function and risk scoring: NYHA cardiac function classification, left ventricular ejection fraction, EuroSCORE II score, Cleveland Clinic score, history of cardiac surgery, recent myocardial infarction (MI) history (<3 months).

Clinical history and comorbidities: history of hypertension, diabetes mellitus, chronic kidney disease, cerebrovascular disease, peripheral vascular disease, chronic obstructive pulmonary disease, hepatic insufficiency (Child-Pugh classification), smoking history, and alcohol consumption history.

Preoperative medication history: Record medications used within 24 hours prior to randomization that cannot be safely discontinued, including RAS inhibitors, β -blockers, calcium channel blockers, diuretics, statins, antiplatelet agents, oral hypoglycemic agents or insulin, and nonsteroidal anti-inflammatory drugs (within 48 hours before surgery).

Baseline laboratory tests: serum creatinine, eGFR (CKD-EPI formula), blood urea nitrogen, hemoglobin, platelet count, albumin, myocardial troponin I, NT-proBNP, and high-sensitivity C-reactive protein.

Surgical parameters: Type of surgery, surgical urgency, extracorporeal circulation time, aortic cross-clamping duration, minimum nasopharyngeal temperature, intraoperative red blood cell transfusion volume, intraoperative urine output, and use of vasoactive drugs during surgery.

Previous intervention history: Whether the participant received vagus nerve stimulation, auricular acupuncture, transcutaneous electrical stimulation therapy, or participated in other clinical studies within 1 month prior to enrollment.

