3.3.3 Statistical Analysis Plan

All data in this study were processed using SPSS 26.0 and R 4.3.0 software.

For continuous variables, the Shapiro-Wilk normality test is first performed. Variables conforming to normal distribution are expressed as "mean \pm standard deviation," with intergroup comparisons conducted using the independent samples t-test. Variables not conforming to normal distribution are represented by median values (25th and 75th percentiles), and intergroup comparisons are performed using the Mann-Whitney U rank-sum test. Categorical variables are presented as frequencies (percentages), with intergroup comparisons analyzed using the χ^2 test. If theoretical frequencies do not meet the test requirements, the Fisher exact probability method must be employed.

The primary endpoint of this study was the incidence of AKI within 7 days postoperatively, analyzed based on the intention-to-treat principle. Kaplan-Meier curves were constructed to plot the cumulative incidence of AKI within 7 days postoperatively for both groups, with intergroup comparisons performed using the log-rank test. The Cox proportional hazards regression model was employed to estimate the hazard ratio (HR) and its 95% confidence interval for the ta-VNS group versus the sham stimulation group. A single-factor COX regression model incorporating only grouping variables was first fitted to estimate the crude effect, followed by a multivariate

COX regression model that adjusted for preoperative eGFR (<90 vs. ≥ 90 mL/min/1.73 m²), diabetes history (present vs. absent), left ventricular ejection fraction (<35% vs. $\geq 35\%$), and surgical type (high-risk group [valve and coronary artery combined/aortic surgery] vs. low-risk group [valve and septal repair]) as covariates. Under the random missingness assumption, imputation models were constructed based on covariates related to outcomes and missingness states, generating 20 imputed datasets for analysis, with results combined according to the Rubin rule. Under the non-random missingness assumption (all missing values in the ta-VNS group were AKI, while all missing values in the sham stimulation group were non-AKI), intergroup comparisons were re-evaluated.

The severity of AKI was analyzed using multivariate ordered logistic regression, adjusting for the same covariates as in the primary analysis and testing the proportional hazards assumption. Results were reported as odds ratios (OR) and their 95% confidence intervals (CI).

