The proportion of patients requiring RRT during hospitalization was compared between groups using χ^2 test or Fisher's exact probability method; the duration of RRT was compared between groups based on its distribution characteristics using independent samples t-test or Mann-Whitney U test.

The proportion of patients with persistent AKI was compared between groups using the χ^2 test; the time to renal function recovery was plotted as cumulative recovery curves using the Kaplan-Meier method, with intergroup comparisons performed via the log-rank test. Patients who did not recover during the observation period were treated as censored data.

Serum creatinine and eGFR at 30 days postoperatively were compared between groups using independent samples t-test or Mann-Whitney U test based on their distribution characteristics.

HRV was analyzed using generalized estimating equations, with grouping, time points, and their interaction terms included as fixed effects. The optimal working-related matrix structure was selected based on the quasi-likelihood independence criterion. Significant group \times time interaction terms indicated statistically distinct temporal trends in HRV metrics between the two groups.

The duration of mechanical ventilation, peak/mean values of vasoactive drug index, peak/mean values of postoperative 48-hour pain NRS scores, and total opioid consumption were compared between groups using independent samples t-test or Mann-Whitney U test based on

their distribution characteristics. The incidence of delirium was compared between groups using χ^2 test. MMSE, QoR-15, and RCSQ were analyzed using generalized estimating equations (GEE), with model specifications identical to those used for HRV analysis.

The incidence rates of new-onset atrial fibrillation, pulmonary infection, stroke, and 30-day all-cause mortality were compared between groups using χ^2 test or Fisher's exact probability method. If the number of events was sufficient, Cox proportional hazards regression model could be employed for analysis, with adjustment for covariates when necessary. Hazard ratios (HR) and their 95% CI were reported.

Hospitalization duration and ICU stay duration were treated as continuous variables, which were expected to follow a skewed distribution. Between-group comparisons were performed using the Mann-Whitney U test. The re-admission rate due to complications was compared using the χ^2 test.

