GEE were employed to analyze differences in the temporal variation trajectories of routine laboratory parameters and plasma IL-6/NGAL levels between two groups. The model included grouping, time, and their interaction as fixed effects, with subjects as random effects. Appropriate work-related matrices and distribution families were selected to assess the significance of the group \times time interaction. Independent samples t-test or Mann-Whitney U test was used to compare postoperative monocyte α 7nAChR expression levels, intracellular IL-6+ proportion, and Th17/Treg ratio at various time points between the two groups. GEE analysis was also conducted to evaluate overall trends and intergroup differences. Spearman correlation analysis was employed to investigate associations between immune cell markers (α 7nAChR, IL-6+, Th17/Treg), plasma biomarkers (IL-6, NGAL), and clinical outcomes (AKI incidence rate, peak serum creatinine level).

[figure not shown]
To determine the minimum number of stimulation days required to achieve clinical efficacy, the completion of stimulation was defined as when the actual daily stimulation duration reached $\geq 80\%$ of the planned duration. Based on the total number of days (0-6 days) during which subjects completed stimulation, a multivariate logistic regression analysis was performed to examine the dose-response relationship between cumulative stimulation days and the incidence of AKI, thereby identifying the critical number of days when the protective effect tends to plateau.

Subgroup analysis was conducted based on the following prespecified factors: gender, left ventricular ejection fraction (<35% vs. $\geq 35\%$), age (<65 years vs. ≥ 65 years), preoperative eGFR (<90 vs. ≥ 90 mL/min/1.73 m²), CPB duration (<120 min vs. ≥ 120 min), and surgical type (high-risk group [valve and coronary artery combined/aortic surgery] vs. low-to-moderate risk group [valve and septal repair]). Subgroup analysis was implemented in single-factor logistic regression models by introducing interaction terms between grouping and subgroup variables, with OR values and 95% CI for each subgroup visually presented in forest plots.

Safety analysis was based on the safety dataset (all subjects who received at least one stimulation). The incidence rates of all adverse events and serious adverse events were compared between groups using the χ^2 test or Fisher's exact probability method.

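### Day-30 creatinine and eGFR should be adjusted for the baseline values already collected, and the laboratory and biomarker model must be named as either a GEE or a mixed model, with small-sample inference in the 40-patient subset

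*Combined protocol and SAP*

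**What the plan says.** Secondary outcome 4 in section 3.3.2.2 is "Serum creatinine and eGFR at 30 days postoperatively". Section 3.3.3 analyses it as follows: "Serum creatinine and eGFR at 30 days postoperatively were compared between groups using independent samples t-test or Mann-Whitney U test", with the choice between the two tests depending on the distribution. The general rule is "For continuous variables, the Shapiro-Wilk normality test is first performed". No covariate, change from baseline, effect estimate or confidence interval is named for this outcome. Section 3.3.2.3 lists the values that could be used, to be completed before randomization: "Baseline laboratory tests: serum creatinine, eGFR (CKD-EPI formula), blood urea nitrogen".

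For the repeated measures, section 3.3.3 has two descriptions:

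- **HRV, and by reference MMSE, QoR-15 and RCSQ:** "HRV was analyzed using generalized estimating equations, with grouping, time points, and their interaction terms included as fixed effects", with a working correlation structure chosen by a quasi-likelihood criterion. Random effects are not mentioned.
- **Routine laboratory values and plasma IL-6/NGAL:** also a GEE, but "The model included grouping, time, and their interaction as fixed effects, with subjects as random effects", followed by a choice of working matrix and distribution family.

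HRV "signals were collected preoperatively and at 24 hours, 48 hours, and 72 hours postoperatively". MMSE, QoR-15, RCSQ and the routine laboratory values also have a preoperative measurement. IL-6, NGAL and the flow-cytometry markers are listed at 24, 48 and 72 hours after surgery only, in an exploratory subset of 40 patients.

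**The concern.** There are three separate issues.

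1. A patient's day-30 eGFR depends in part on the eGFR with which that patient came to surgery. The baseline value is in hand, and leaving it out keeps that between-patient variance in the comparison. The trial is sized for AKI only, so precision on this outcome has not been provided for in any other way.
2. A GEE is a marginal model with a working correlation, and a mixed model has subject random effects. The wording for the laboratory values and biomarkers asks for both. Two analysts could fit different models and each claim to have followed the plan. If the GEE is fitted with its default sandwich variance in about 20 patients per arm, the test rejects too often.
3. For outcomes with a preoperative measurement, the plan does not say whether that value is a covariate, a time point with a free group difference, or a time point constrained to be equal between groups. These choices give different estimates and different precision.

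**Working it through.** **Inputs from the documents.** Section IV gives 68 evaluable and 76 enrolled per arm, 10% dropout, two-sided alpha 0.05, power 0.80 and AKI rates of 17.1% and 37.9%. Section 3.3.2.2 gives the 40-patient subset (about 20 per arm) and three postoperative samples. The documents give no SD and no baseline-to-day-30 correlation (rho), so rho is an assumption and is shown as a range.

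**The plan's own figure.** The two-proportion formula with unpooled variance gives (1.960 + 0.842)² × (0.171 × 0.829 + 0.379 × 0.621) / 0.208² = 68.4, or 69 per arm against the stated 68. Dropout: 68 / 0.90 = 75.6, so 76. The stated size reproduces to within one patient. I use 68 per arm below and assume that the same number has a day-30 value.

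**Day 30.** Relative to the unadjusted comparison, the variance of the baseline-adjusted difference is 1 − rho², and the equivalent unadjusted size is 68 / (1 − rho²). The difference detectable with 80% power, in SD units, is 2.80 × √(2/68) = 0.48 unadjusted, and 0.48 × √(1 − rho²) adjusted.

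| rho (assumed) | variance cut | equivalent n per arm | detectable difference (SD) |
|---|---|---|---|
| 0.3 | 9% | 75 | 0.46 |
| 0.5 | 25% | 91 | 0.42 |
| 0.7 | 49% | 133 | 0.34 |
| 0.8 | 64% | 189 | 0.29 |

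The type I error does not move. In 60,000 simulated trials per rho at 68 per arm, it was 4.9% to 5.2% for the t-test and 4.9% to 5.1% for the adjusted model. The Shapiro-Wilk two-stage rule held 5.05% with lognormal data.

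**GEE in the subset.** Take complete normal data and a separate mean for each group and visit. The uncorrected sandwich estimate then uses divisor n rather than n − 1 in each arm, so the Wald statistic is n/(n − 1) times Hotelling's T². With n = 20, three visits (2 df for group by time) and 38 error df, the chi-square cut-off of 5.99 corresponds to F(2, 37) = 5.99 × (38/40) × 37/(2 × 38) = 2.77. The tail probability is 7.6%. Simulations with exchangeable correlation 0.5 or 0.6 gave 7.45% to 7.9%.

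The same formula at 68 per arm gives 6.0% for four time points (HRV) and 7.6% for eight (routine laboratory values: preoperative plus seven days; simulation gave 7.1%). The excess comes from the number of patients relative to the degrees of freedom tested. It does not come from leaving out baseline.

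**Role of the preoperative value.** If it is a free time point, the group-by-time contrast is in effect a change from baseline, with variance 2(1 − rho). As a covariate, the variance is 1 − rho². The ratio is (1 + rho)/2, which is 0.75, 0.85 and 0.90 at rho 0.5, 0.7 and 0.8.

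**The case against.** The strongest reply is that the planned day-30 comparison is valid. Randomization makes it unbiased, its error rate is correct, and chance imbalance at baseline is ordinary sampling error that the test already allows for. All of this stands. A reader might infer that the day-30 tests misstate their error; they do not, and the only cost is power and interval width. It is also fair that requiring eGFR of at least 60 narrows the baseline range and could lower rho. For that reason the table starts at 0.3, where the gain is only 9%.

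Three further inferences go too far:

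- **That every repeated-measures model has the random-effects fault.** The phrase appears only for routine laboratory values and IL-6/NGAL. The GEE for HRV, MMSE, QoR-15 and RCSQ is coherent as written.
- **That the plan ignores baseline throughout.** The adjusted Cox and AKI-severity models include preoperative eGFR (dichotomised at 90). For the repeated measures, the natural reading is that the preoperative value is one of the time points. The gap there is an unstated role, and the remaining gain is modest.
- **That GEE should be abandoned.** At 68 per arm and four time points, the error is about 6%. A mixed model is an acceptable alternative, but preferring it is a matter of taste. Nor does it settle missing questionnaires in sedated patients if missingness depends on their unobserved state.

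It can also be said that the laboratory and biomarker sentence is recognisably a GEE with one stray phrase. That is likely, but the plan should not leave the analyst to decide.

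**Conclusion.** The point holds for secondary and exploratory outcomes.

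- **Day-30 creatinine and eGFR:** a free improvement. The planned test is sound but discards precision worth 9% to 64% of the variance over assumed correlations of 0.3 to 0.8. The size rests on that assumption and on 68 evaluable patients per arm; the direction does not depend on the value chosen within the range.
- **Routine laboratory values and IL-6/NGAL:** wrong as written, because the model described mixes two incompatible types. If it is run as an uncorrected GEE in the 40-patient subset, the group-by-time test has about 7.5% type I error at a nominal 5%, assuming complete, roughly normal data.
- **Repeated measures with a preoperative value:** the role of that value needs stating. Using it as a covariate gives 0.75 to 0.90 of the change-from-baseline variance at correlations of 0.5 to 0.8.

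The primary AKI analysis and the sample size are untouched.

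**What to change.** 1. **Day 30.** Replace the normality-gated test with a linear model of eGFR, and of log creatinine, on group, the continuous baseline value of the same measure and the Cleveland Clinic stratum used in randomization. Report the adjusted difference with its 95% CI (a ratio for creatinine).
2. **Routine laboratory values and IL-6/NGAL.** Name one model: either a GEE with a working correlation and no random effects, or a linear mixed model with its covariance structure stated.
3. **The 40-patient subset.** Use a bias-corrected sandwich with a small-sample reference distribution, or a mixed model with Kenward-Roger degrees of freedom. Include no baseline term, because no preoperative sample is listed for these markers. The same correction is worth applying to the eight-time-point laboratory models.
4. **HRV, MMSE, QoR-15, RCSQ and routine laboratory values.** Enter the preoperative value as a covariate, or constrain it to be equal between groups, rather than as a free time point. GEE may be kept.

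The cost is a few sentences in section 3.3.3 and a few lines of R, which the plan already uses. No new samples, visits or patients are needed. The change should be made before unblinding.

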**Office Title: Transcutaneous Auricular Vagus Nerve
Stimulation for Preventing Acute Kidney Injury in Patients
Undergoing Cardiac Surgery With Cardiopulmonary
Bypass: A Randomized Controlled Trial
NCT number: Not yet assigned
Protocol Number: 20260315122240876
Version: V1.0
Version date: February 6, 2026**

Transcutaneous Auricular Vagus Nerve Stimulation for Preventing Acute Kidney Injury in Patients Undergoing Cardiac Surgery With Cardiopulmonary Bypass: A Randomized Controlled Trial

Research Protocol

I. Research Background

Acute kidney injury (AKI) is one of the most common and severe complications following cardiac surgery, characterized by a rapid decline in renal function within hours to days [1-3]. Despite continuous advancements in cardiac surgical techniques, the incidence of postoperative AKI remains as high as 10.4% – 42%, with approximately 2% – 3% of patients requiring renal replacement therapy [2-7]. AKI not only significantly prolongs patients' time in the intensive care unit (ICU) and overall hospital stay but is also strongly associated with increased 30-day and long-term mortality rates, posing a major threat to patient prognosis [2,4]. Cardiopulmonary bypass (CPB), as a critical technical support for cardiac surgery, can induce ischemia-reperfusion injury, systemic inflammatory responses, and autonomic dysfunction due to non-physiological perfusion [8-11], leading to a further increase in the incidence of CPB-associated AKI to 20.8% – 50.8%. The risk is significantly positively correlated with CPB duration and is particularly prominent in complex surgeries [2-6,12-18].

Regarding the prevention of CPB-associated AKI, current clinical strategies primarily focus on perioperative hemodynamic optimization, volume management, and pharmacological interventions. However, these measures are predominantly supportive in nature and fail to fundamentally prevent the onset and progression of AKI [9,19,20]. Although previous studies have explored various pharmacological and blood purification interventions, there remains a lack of highly evidence-based specific therapies with robust high-level evidence [21-23]. This situation

highlights the fundamental limitations of current prevention strategies centered on systemic hemodynamic support and nonspecific anti-inflammatory measures, underscoring the urgent need for novel intervention strategies targeting new mechanisms and targets to overcome the challenges in AKI prevention.

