the Confusion Assessment Measure (CAM) or the ICU Confusion Assessment Measure (CAM-ICU) for both preoperative and postoperative periods (over 7 consecutive days). Early cognitive function was screened using the Mini-Mental State Examination (MMSE) on preoperative day 1, postoperative day 3, and postoperative day 7. Sleep quality was evaluated using the Richards-Campbell Sleep Questionnaire (RCSQ) on preoperative day 1, postoperative day 1 morning, and postoperative day 3 morning to assess prior night sleep status. Recovery quality was scored using the 15-item Quality of Recovery Scale (QoR-15) on preoperative day 1, postoperative day 1, postoperative day 3, and postoperative day 7. Pain and analgesic demand were recorded as baseline pain levels on preoperative day 1 and pain numerical scores (NRS) within 48 hours postoperatively (recorded at least once daily), along with total opioid consumption within 48 hours postoperatively (converted to oral morphine equivalents).

7) Perioperative complications and mortality rate

The incidence rates of cardiovascular complications (including new-onset atrial fibrillation and other arrhythmias, acute myocardial infarction, postoperative myocardial injury, and low cardiac output syndrome), stroke, pulmonary embolism, pulmonary infection, deep vein thrombosis, surgical site deep infection, and all-cause mortality within 30 days postoperatively.

8) Resource consumption

Length of hospital stay, ICU stay duration, and re-admission rate due to complications.

9) Biomarkers

To comprehensively evaluate patient status and explore the pathogenesis of AKI, this study detected the following biomarkers:

a) Routine testing: Collect daily routine laboratory data before surgery and for 7 days postoperatively, including C-reactive protein (CRP), neutrophil-to-lymphocyte ratio (NLR), cardiac troponin (cTn), creatine kinase isoenzyme MB (CK-MB), N-terminal pro-brain natriuretic peptide (NT-proBNP), and serum cystatin C.

b) Specific inflammatory markers and renal injury indicators: Peripheral blood samples were collected at 24h, 48h, and 72h postoperatively and placed in EDTA anticoagulation tubes. Plasma interleukin-6 (IL-6) and neutrophil gelatinase-associated lipocalin (NGAL) concentrations were detected in batches using the ELISA method.

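### Hospital stay, ICU stay and renal recovery have no rule for patients who die; the recovery curve may overstate recovery, and the stay comparison is open to a bias of unknown direction

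*Combined protocol and SAP*

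**What the plan says.** Stay is listed in 3.3.2.2, item 8 (Resource consumption): "Length of hospital stay, ICU stay duration, and re-admission rate due to complications". No definition is given for a patient who dies before discharge. In 3.3.3 the analysis reads "Hospitalization duration and ICU stay duration were treated as continuous variables", with skewness anticipated, followed by "Between-group comparisons were performed using the Mann-Whitney U test".

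Recovery is defined in 3.3.2.2, item 3, for patients with AKI: "The time from diagnosis to the first recovery of serum creatinine to within 1.5 times the baseline level without the need for RRT". In 3.3.3, "the time to renal function recovery was plotted as cumulative recovery curves using the Kaplan-Meier method", the arms are compared by log-rank test, and "Patients who did not recover during the observation period were treated as censored data". Neither the length of the observation period nor the time at which a patient is censored is stated.

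Death appears only as a separate 30-day secondary outcome. The documents contain no worst-rank rule, no days-alive measure, no restriction to survivors and no competing-risk method. The missing-data rules in 3.3.3 sit within the primary AKI analysis and do not reach these outcomes.

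**The concern.** Applied as written, a patient who dies in hospital on day 2 has a 2-day stay and gets one of the best ranks, ahead of a patient with an uncomplicated 12-day stay. The same patient cannot be readmitted and so counts as a success there too.

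For recovery, an AKI patient who dies unrecovered falls under the censoring sentence. If the censoring time is the date of death, Kaplan-Meier assumes that this patient would have gone on to recover at the rate of those still under observation. One minus the Kaplan-Meier estimate is then not the proportion who recovered.

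Death is unlikely to be unrelated to treatment if the trial's premise is right: the Research Background describes AKI as "strongly associated with increased 30-day and long-term mortality rates". Without a rule, the choice between analyses that can point in different directions is left until the data are in hand.

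**Working it through.** **The plan's own figures.** The plan gives no power, mortality, stay or recovery figures for these outcomes. Its only related figure is the sample size. For 17.1% against 37.9%, two-sided 0.05 and 80% power, the unpooled normal approximation gives 68.4 per arm, close to the stated 68. Then 68/0.9 = 75.6, hence 76 per arm. That is not in dispute. The planned rates imply 0.379 × 76 ≈ 29 sham and 0.171 × 76 ≈ 13 ta-VNS patients with AKI.

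**Recovery, worked example (assumed course).** Take the 29 sham AKI cases. Ten recover, then 3 die unrecovered, then 8 of the remaining 16 recover.
- Censored at death: 1 − (19/29) × (8/16) = 0.672.
- Actual proportion recovered: 18/29 = 0.621.
- Deaths kept in the risk set as non-recovered: 1 − (19/29) × (11/19) = 18/29 = 0.621, so the overstatement disappears.

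**Recovery, both arms (assumed constant hazards).** Recovery hazard r = 0.1 per day in both arms; death hazard d = 0.005 (ta-VNS) and 0.02 (sham). Censoring at death shows 1 − exp(−rT). The true cumulative incidence is r/(r+d) × [1 − exp(−(r+d)T)].

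| Window T | Shown, both arms | True, ta-VNS | True, sham |
|---|---|---|---|
| 7 days | 50.3% | 49.6% | 47.4% |
| 30 days | 95.0% | 91.2% | 81.1% |

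The size depends heavily on the window, which the plan does not state.

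**Stay, formula.** Suppose that survivors' stays have the same distribution in both arms. Let m_s and m_t be in-hospital mortality in sham and ta-VNS, and q the probability that a patient who dies has a shorter recorded stay than a survivor. Summing over the four combinations of death and survival, with ties between two deaths split evenly:

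P(ta-VNS patient has the shorter stay) = 0.5 − (m_s − m_t)(q − 0.5).

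There is no bias if mortality is equal, or if q = 0.5. The sign turns on whether q exceeds 0.5, that is, on death timing relative to usual stay. Ranking death worst is the case q = 0.

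**Stay, numbers.** Assumed: mortality 4% sham and 2% ta-VNS, log-normal stay with log-SD 0.4, deaths uniform over the stated days.

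| Setting | q | Index |
|---|---|---|
| Median 12 days, deaths on days 1–8 | 0.97 | 0.5 − 0.02 × 0.47 = 0.491 |
| Median 12 days, deaths on days 1–30 | 0.41 | 0.5 + 0.02 × 0.09 = 0.502 |
| ICU, median 3 days, deaths on days 1–8 | 0.32 | 0.5 + 0.02 × 0.18 = 0.504 |
| Death ranked worst | 0 | 0.5 + 0.02 × 0.5 = 0.510 |

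Simulation with 76 per arm agrees: 0.490 to 0.492 for the first row, 0.502 for the second, and 0.501 to 0.511 across runs with a 3-day ICU median. At these rates the expected deaths are about 0.04 × 76 = 3 sham and 0.02 × 76 = 1.5 ta-VNS.

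**The case against.** A reader might infer that the plan is biased against ta-VNS and loses substantial power on stay. The documents do not support that.

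- **Direction.** It requires more deaths in sham and deaths that come early relative to usual stay. The documents give neither mortality nor death timing. A death after a long ICU course counts as a long stay, and the second and third settings above lean very slightly towards ta-VNS.
- **Power.** With a true 15% shorter stay and deaths on days 1 to 8, simulated power as written is about 63%, 56% and 51% at sham against ta-VNS mortality of 2% v 1%, 4% v 2% and 6% v 3%; with death ranked worst it is about 68%, 71% and 72%. With deaths over days 1 to 30, power as written is 64% to 68%, against 68% with no deaths. Survivors-only power is 65% to 70%, so part of the gap is mortality signal added by worst ranking and not stay signal lost.
- **Estimand.** Stay is listed as resource use, and a patient who dies on ICU day 2 did use two ICU days. Raw duration is coherent for that purpose, and mortality is tested separately.
- **Recovery.** The plan does not mention deaths or a censoring time. Censoring at the end of the window is a natural reading and largely avoids the overstatement. The log-rank test remains valid for the cause-specific recovery hazard either way.
- **Few deaths are plausible.** Surgery is elective, eGFR is at least 60, ASA and NYHA are I to III, and critically ill patients are excluded.

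All of this stands. It limits the size and removes any claim about direction. It does not supply the missing rule, and raw duration still cannot be read as a sign of faster recovery when early deaths count as short stays.

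**Conclusion.** The gap is real and minor. An early in-hospital death is ranked as a short hospital stay. The cumulative recovery curve overstates the proportion recovered if unrecovered deaths are censored at death: 67% against 62% in the single-arm example, and between 1 and 14 percentage points per arm in the constant-hazard example, according to arm and window. For stay, at 4% against 2% mortality the index is about 0.49 as written and 0.51 with death ranked worst if deaths are early; it is practically 0.50 if they are spread over 30 days, and slightly above 0.50 for a short ICU stay. All mortality, stay, timing and recovery inputs are assumptions. The error in recovery lies in reading the curve as a proportion recovered, not in the log-rank test. Only secondary outcomes are involved; the primary AKI conclusion is not affected by this point.

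**What to change.** **Recovery.** State the observation window and the censoring time. Estimate the cumulative incidence of recovery with death without recovery as a competing event, compared by Gray's test. Alternatively, keep such patients as non-recovered to the end of the stated window.

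**Hospital and ICU stay.** Add a Mann-Whitney analysis in which in-hospital deaths take the worst rank, and report it beside the raw duration and the duration in survivors. State in one line how deaths enter the readmission rate and the RRT and ventilation durations, which have the same gap.

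**Cost.** This is SAP wording, to be settled before unblinding. Stay and 30-day mortality are already outcomes; the date of death and whether it occurred in hospital must be available. The downside is that the worst-rank version combines death with duration, so it must not be read as resource use alone. That is why the raw and survivor figures should stand beside it.
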